| 10.4 | Study Discontinuation..... | 19 |
| 11 | REFERENCES..... | 19 |

PRÉCIS

Study Title

The Promotion of Physical Activity for the Prevention of Alzheimer's Disease in Adults with Down Syndrome

Objectives

Primary aim: Assess daily moderate-to-vigorous physical activity (MVPA, min) in the Remote Low (RL), Remote High (RH), and Usual Care (UC) arms at baseline, 3, 6, 9, and 12 mos., and obtain effect sizes for change in MVPA over 12-mos.

Secondary aim 1: Assess the impact of MVPA across the RL, RH, and UC arms on cardiovascular fitness, quality of life, cognitive function and brain parameters related to AD (whole and regional brain volume, functional connectivity, cerebral blood flow) at baseline, 6, and 12 mos.

Secondary Aim 2: Determine the feasibility (retention, session attendance, use of recorded sessions (RH/RL only) and safety of RL, RH, and UC arms.

Design and Outcomes

This is a 12-mo. trial in 80 non-demented adults with Down Syndrome. Participants will be randomized (2:2:1) to attend 40 min. remotely delivered group MVPA sessions (Zoom™ Video Conferencing Inc., San Jose, CA) at a low frequency (1 session/wk., RL) or high frequency (3 sessions/wk., RH), or a usual care control (UC). In addition to the group MVPA sessions, participants in both the RL and RH arms will receive a step counter (Charge 3™, Fitbit, San Francisco, CA), access to resources for increasing MVPA, and two 20-min remotely delivered (Zoom™) individual support/education session/mo. Content for both the RL and RH arms will be identical with the exception of group MVPA session frequency (1 vs. 3/wk.). Participants in the UC arm will receive a step counter (Charge 3™, Fitbit, San Francisco, CA), access to resources for increasing MVPA, and bi weekly remote (Zoom™) individual support/education). Daily MVPA will be assessed by portable accelerometer (ActiGraph wGT3XBT, ActiGraph LLC, Pensacola, FL) at baseline, 3, 6, 9 and 12 mos. All secondary outcomes will be assessed at baseline, 6 and 12 mos.

| Table 1: Design Overview | | | |
|--|--|-----------------------------|--------------------------|
| | Intervention Arms | | |
| | Remote High | Remote Low | Usual Care |
| MVPA recommendation | 150 min/wk. | 150 min/wk. | 150 min/wk. |
| Group MVPA sessions | Yes | Yes | No |
| Delivery format | Zoom™ video conferencing | Zoom™ video conferencing | NA |
| Frequency | 3d/wk. | 1d/wk. | NA |
| Intensity | ≥ 3 METS | ≥ 3 METS | NA |
| Duration | 40 min | 40 min | NA |
| Content | Stretch/aerobic activity/RE | Stretch/aerobic activity/RE | NA |
| Access to PA resources | Yes | Yes | Yes |
| MVPA Self-monitoring | Fitbit | Fitbit | Fitbit |
| Education/support/feedback sessions | Yes | Yes | Yes |
| Participants | DS adult + Study Partner | DS adult + Study Partner | DS adult + Study Partner |
| Frequency | 2x/mo | 2x/mo | 2x/mo |
| Delivery format | Zoom™ | Zoom™ | Zoom™ |
| Duration | 20 min/session | 20 min/session | 20 min/session |
| | Note: NA = not applicable, RE= resistance exercise | | |

Interventions and Duration

Participants will be randomized to one of 3 interventions for 12 months.

1. Remote High (RH)
2. Remote Low (RL)
3. Usual Care (UC)

Sample Size and Population

80 adults (≥ 18 years of age) with Down syndrome will be recruited and computer randomized. Participants will be stratified by sex and then sequentially randomized by the study statistician with 2:2:1 allocation to the RL, RH, and UC arms. We expect 32 participants in the RL, 32 participants in RH, and 16 in UC.

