4.3 Study Enrollment Procedures

Project staff will contact local community agencies serving adults with DS, case managers, and CDDOs by mail/email, provide presentations at CDDO meetings, and text for CDDO newsletters describing the project. Interested parents/guardians, caregivers, or adults with DS will be asked to contact the study coordinator via email, our website (www.ebl.ku.edu), or a dedicated toll-free study phone number that will be included in all recruitment materials. The study coordinator will contact the interested individuals by phone to answer questions and conduct an initial eligibility screen. Zoom calls will be scheduled with those remaining interested, and potentially eligible, to obtain informed consent (participants or guardian and caregivers) and assent (participant) and determine final eligibility based on the DSQIDD scores. Project staff will send a form (fax/email) to the potential participant's PCP which describes the study and requests clearance for participation. Participants found to be ineligible will be provided with written materials describing available resources for increasing physical activity. Project staff will track ineligibility and non-participants of eligible candidates using a REDCAP database. Participants will be stratified by sex and then sequentially randomized by the study statistician with 2:2:1 allocation to the RL, RH, and UC arms.

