5 STUDY INTERVENTIONS

Randomization Cohorts of ~10-20 participants will be recruited and computer randomized. Participants will be stratified by sex and age (18-30 or >30) and then sequentially randomized by the study statistician with 2:2:1 allocation to the RL, RH, and UC arms. This randomization scheme was selected to include more participants in the group video conferencing arms which, if successful, will be included in a later stage trial examining the effectiveness of increased MVPA using the video conferencing approach on cognitive function and brain health in adults with DS. Intervention assignments will be concealed in envelopes and delivered to the study coordinator.

Caregiver role. We will recruit either a parent/guardian or residential support staff, to serve as a study partner for each participant. Study partners will be allowed to assist multiple adults, provided all adults are in the same intervention group. Study partners will be asked to attend all individual support/education sessions, and to support, encourage, and assist participants in complying with the study protocol, such as reminding them to attend the group exercise sessions (RL and RH only), individual support session (all groups) providing opportunities for increased MVPA, and assisting with self-monitoring of MVPA.

MVPA recommendations. We will target 150 min/wk. of MVPA (≥ 3 METs) for all groups as recommended for all adults by the American College of Sports Medicine ¹ and the U.S. Department of Health and Human Services ². MVPA recommendations will progress from 60 min/wk. (3 d/wk., 20 min./d) to 150 min./wk. (5 d/wk., 30 min./d) at the beginning of mo. 4, and remain at 150 min./wk. through the end of the study. Accumulated MVPA in bouts ≥ 10 min will be permitted.

RL and RH Intervention.

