8 STATISTICAL CONSIDERATIONS

8.1 Sample Size and Randomization

Eighty participants will be randomized in a 2:2:1 manner to RH (n=32), RL (n=32) and UC (n=16), respectively. We except a standard deviation in daily MVPA of ~ 10 min. for our primary endpoint (12 mos.) based on 12 mo. data from adults with DS who participated in our weight management trial in adults with IDD (DK83538, PI [name]). We will be able to estimate the mean MVPA at each time point (baseline, 3, 6, 9 and 12 mos.) with 99% confidence within ± 5 min. for the RH and RL groups with 32 participants, and with 98% confidence with 24 participants, i.e. allowing for a 25% loss to follow-up. We will be able to estimate the mean MVPA at each time point with 94% confidence within ± 5 min. for the UC group with 16 participants, and with 89% confidence with 12 participants, i.e. allowing for 25% loss to follow-up). Thus, we will have precision to estimate the intervention effects even with a 25% loss to follow-up.

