8.1.1 Treatment Assignment Procedures

Cohorts of ~10-20 participants will be recruited and computer randomized. Participants will be stratified by sex and age (18-30 or >30) and then sequentially randomized by the study statistician with 2:2:1 allocation to the RL, RH, and UC arms.

This randomization scheme was selected to include more participants in the group video conferencing arms which, if successful, will be included in a later stage trial examining the effectiveness of increased MVPA using the video conferencing approach on cognitive function and brain health in adults with DS.

Intervention assignments will be concealed in envelopes and delivered to the study coordinator. Participant randomization will be stored on the study Redcap Database.

The study team and the participants will not be blinded to group assignment.

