8.3 Data Analyses

Our primary aim is to assess daily MVPA (min.) among the RL, RH, and UC arms at baseline, 3, 6, 9, and 12 mos. and obtain effect sizes for change in MVPA over 12-mos. We will calculate the mean and standard deviation and 95% confidence intervals of daily MVPA at each time point for all 3 groups, as well as for the change from baseline to each time point. This descriptive information will be summarized graphically which will aid in determining if, and when, differences in MVPA arise among and across the 3 groups. The corresponding effect sizes at each time point will be calculated as the differences in the mean divided by the common standard deviation. We will also estimate the correlation of MVPA over time within individuals. This information will be critical to identifying whether single point in time or longitudinal assessments will be utilized to identify the sample size needed for future large-scale confirmatory trials. We will subsequently run a repeated measures ANOVA comparing the change in baseline at each time point across the three groups using a linear mixed model approach with an autoregressive correlation structure over time. The model will include a main effect of group and time and a group by time interaction which will provide an estimate of the treatment effect when modeling longitudinally. The data from this trial will provide solid preliminary data to determine the potential for an effect and inform the best design to employ in subsequent trials.

Our first secondary aim will assess the impact of MVPA across the RL, RH, and UC arms on cardiovascular fitness, quality of life, cognitive function, and brain parameters (whole and regional brain volume, functional connectivity, cerebral blood flow) at baseline, 6, and 12 mos. We will estimate the correlation of change in MVPA on changes in cardiovascular fitness, quality of life, cognitive function, whole and regional brain volume, functional connectivity and cerebral blood flow at 6 and 12 mos. This analysis will be completed with the total sample, irrespective of study arm. Thus 80 participants will provide at least 80% power to detect correlation of 0.31 or higher or -0.31 or lower with a type I error rate of 5%. Sixty subjects (25% loss to follow-up) will still allow us to detect a correlation of 0.36 or higher or -0.36 or lower with 80% power and type I error rate of 5%.

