Our second secondary aim will determine the feasibility (retention, session attendance, use of recorded sessions (RH/RL only), and safety) of RL, RH, and UC arms. We will estimate the proportion of participants retained, session attendance, use of recorded sessions and safety, i.e. significant adverse events across the 12 mo. trial, the proportion that adhere to treatment within each arm. Within the RL and RH arms, 32 participants allow us to estimate these proportions with a margin of error no greater than 0.09. Within the UC group, 16 participants will allow us to estimate these proportions with a margin of error no greater than 0.125.

For all analysis we will explore the impact of demographic characteristics such as gender, and racial/ethnic subgroups.

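### The protocol gives two different stratification schemes (sex only; sex and age group), and the one between-arm model pre-specifies none of the factors

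*Combined protocol and SAP*

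**What the plan says.** Four places describe the same randomization step, in two versions.

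- PRÉCIS, Sample Size and Population: "Participants will be stratified by sex and then sequentially randomized by the study statistician with 2:2:1 allocation".
- Section 4.3, Study Enrollment Procedures: "Participants will be stratified by sex and then sequentially randomized by the study statistician with 2:2:1 allocation to the RL, RH, and UC arms".
- Section 5, Study Interventions (Randomization): "Participants will be stratified by sex and age (18-30 or >30) and then sequentially randomized".
- Section 8.1.1, Treatment Assignment Procedures: the same wording as Section 5, with sex and age group.

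The sizes are given in Section 8.1: "Eighty participants will be randomized in a 2:2:1 manner to RH (n=32), RL (n=32) and UC (n=16), respectively". Recruitment is in batches: "Cohorts of ~10-20 participants will be recruited and computer randomized" (Section 8.1.1). No block size is given.

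For the analysis, Section 8.3 specifies one between-arm model, a linear mixed model for change in MVPA with an autoregressive correlation structure: "The model will include a main effect of group and time and a group by time interaction". The closing sentence of Section 8.3 adds: "For all analysis we will explore the impact of demographic characteristics such as gender, and racial/ethnic subgroups". That sentence names gender but not age, gives no model form, and does not mention stratification factors.

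**The concern.** A statistician who builds the allocation list from Section 4.3 gets two strata; one who works from Section 8.1.1 gets four. The scheme cannot be reproduced from the document, and a later reader cannot tell whether age was balanced by design or left to chance.

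The analysis does not settle the matter. Factors used to restrict a randomization normally enter the model that compares the arms, because otherwise the reported standard errors ignore the balance that the restriction created. Here neither version is carried into the MVPA model. With 16 people in UC, chance imbalance on a factor that is not stratified can be sizeable, and the trial's product is a set of effect sizes and intervals for planning a later trial. Arm comparability and honest interval width are therefore what is at stake.

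**Working it through.** **1. The plan's own figures, and whether they depend on this point.** Section 8.1 assumes an SD of about 10 min and a margin of 5 min. The confidence is 2·T(n−1)[5/(10/√n)] − 1, with T the t distribution function.

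| n | 5/(10/√n) | Recomputed | Stated |
|---|---|---|---|
| 32 | 2.83 | 99.2% | 99% |
| 24 | 2.45 | 97.8% | 98% |
| 16 | 2.00 | 93.6% | 94% |
| 12 | 1.73 | 88.9% | 89% |

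The correlation power in Section 8.3 also reproduces (Fisher z, two-sided 5%): 80.3% for r = 0.31 at n = 80 and 81.2% for r = 0.36 at n = 60, against a stated 80%. The allocation is 80 × 2/5 = 32, 32, and 80 × 1/5 = 16. None of these uses the stratification factors, so the contradiction changes no stated number.

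**2. If sex only is used: age balance between RH and UC.** The share aged over 30 is not in the documents; take p = 0.3 to 0.7. The SD of the difference in shares is √[p(1−p)(1/32 + 1/16)].

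- p = 0.5: √(0.25 × 0.09375) = 0.153, and 1.96 × 0.153 = 0.30.
- p = 0.3 or 0.7: √(0.21 × 0.09375) = 0.140, and 1.96 × 0.140 = 0.27.

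A simulation of 80 people (half female, permuted blocks of 5 within strata; both are assumptions) agrees:

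| Scheme | Mean absolute gap | 95th percentile | Gap of 20 points or more |
|---|---|---|---|
| Sex only | 11-12 points | 28-30 points | 15-20% of trials |
| Sex and age | about 3 points | about 7 points | about 0% |

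The second row assumes allocation lists that run across cohorts. Four strata in a cohort of 10-20 average only 10/4 = 2.5 to 20/4 = 5 people, so lists restarted in each cohort would balance less well.

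**3. If sex and age are used but not modelled: reported standard errors.** Let R² be the share of outcome variance that the two factors explain. The unadjusted standard error exceeds the adjusted one by about 1/√(1−R²).

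- R² = 0: 1.00 (no inflation).
- R² = 0.10: 1/√0.9 = 1.054.
- R² = 0.20: 1/√0.8 = 1.118.

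The simulated 12-month comparison (total SD 10) gives 3.060/2.901 = 1.055 at R² = 0.10 and 3.058/2.737 = 1.117 at R² = 0.20. Type I error at a nominal 5%, and power for an assumed RH-UC difference of 8 min, are:

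| R² | Type I, unadjusted | Type I, adjusted | Power, unadjusted | Power, adjusted |
|---|---|---|---|---|
| 5% | 4.4% | 5.5% | 73% | 75% |
| 10% | 4.1% | 4.9% | 74% | 78% |
| 20% | 3.4% | 5.1% | 76% | 83% |
| 30% | 2.2% | 4.7% | 77% | 87% |

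With 4,000 runs per cell, the Monte Carlo standard error of a 5% rate is √(0.05 × 0.95/4000) = 0.3 points, so the adjusted rates are compatible with 5% and the unadjusted ones drift downward.

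**The case against.** The strongest reply is that little hangs on this. The trial is early-stage and mainly descriptive: means, SDs, confidence intervals and effect sizes by arm. Leaving the strata out of the model neither biases a randomized comparison nor inflates type I error. The closing sentence of Section 8.3 plans to look at gender in every analysis, and its list is open-ended. The R² is assumed. The model analyses change from baseline, so if sex and age shift MVPA equally at both times they explain none of the change and the inflation is zero.

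Most of that stands, and it limits the size of the point: the range for the standard errors has to start at 0%. It does not remove the contradiction, and a promise to explore gender does not pre-specify adjustment or cover age.

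Some stronger readings are tempting, but the documents do not support them.

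- *The secondary analyses also fail to match the randomization.* Section 8.3 analyses secondary aim 1 as correlations pooled over arms and aim 2 as proportions within each arm. Neither is a randomized between-arm model. Adjusting the correlations for age would need a separate confounding argument.
- *Age imbalance would distort a comparison of arms on Alzheimer's outcomes, since Section 2.1 puts onset as early as 30 in some people.* The between-arm model is for MVPA; cognition and imaging are analysed pooled. The documents do not show a link between age and MVPA.
- *Stratifying without adjusting throws the balance away.* It does not. The estimate is still less variable: unadjusted power rises slightly, from 73% to 77%, as R² goes from 5% to 30%. Only the reported standard error fails to show it.
- *Both harms occur together.* Age imbalance of the size shown belongs to the sex-only scheme; over-wide standard errors from stratifying on age belong to the other.

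**Conclusion.** The contradiction is certain: two places give sex only, two give sex and age group, and nothing in the text chooses between them. It is equally clear that the stratification factors are not pre-specified in the MVPA model.

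The consequence is moderate and conditional. Under sex only, the risk is a chance age gap between RH and UC, resting on an assumed 30-70% of participants aged over 30; the upper figure of 28-30 points is a 1-in-20 event, not the typical case. Under sex and age, the cost is conservative inference on MVPA, about 0-12% on the standard error for an assumed R² of 0-20%. Adjustment is worth making because it is nearly free, not because the unadjusted comparison would be invalid.

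**What to change.** State one scheme, in the same words, in the PRÉCIS (Sample Size and Population) and in Sections 4.3, 5 and 8.1.1. The two sections that describe randomization in detail both give sex and age group. If randomization has begun, state the scheme actually used. In the same edit it would help to give the block method and to say whether the lists run across cohorts.

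In Section 8.3, add the stratification factors actually used as fixed effects in the MVPA linear mixed model. The secondary analyses need no change on this ground.

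The cost is wording and two degrees of freedom (one if only sex is used). Both variables must be known before a participant can be stratified, so no new data are needed.

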1 STUDY OBJECTIVES

1.1 Primary Objective

Assess daily MVPA (min) in the RL, RH, and UC arms at baseline, 3, 6, 9, and 12 mos., and obtain effect sizes for change in MVPA over 12-mos.

1.2 Secondary Objectives

Secondary aim 1: Assess the impact of MVPA across the RL, RH, and UC arms on cardiovascular fitness, quality of life, cognitive function and brain parameters related to AD (whole and regional brain volume, functional connectivity, cerebral blood flow) at baseline, 6, and 12 mos.

Secondary Aim 2: Determine the feasibility (retention, session attendance, use of recorded sessions (RH/RL only) and safety of RL, RH, and UC arms.

2 BACKGROUND AND RATIONALE

2.1 Background on Condition, Disease, or Other Primary Study Focus

Nearly all individuals with Down Syndrome (DS) will develop Alzheimer's Disease (AD), some beginning as early as age 30. To date, trials have failed to identify any drug that is safe or effective for the prevention of AD in adults with DS, and there is a lack of non-pharmacologic strategies for the prevention of AD in adults with DS. Previous research in typically developing adults suggests that increased MVPA may improve cognitive function and protect against age-related functional and structural brain changes; however, the potential impact of increased MVPA on the development of AD in adults with DS has not been evaluated. Despite the potential positive impact of MVPA, participation in MVPA among adults with DS is low. The limited research evaluating intervention strategies for increasing MVPA in adults with DS is not specific to adults with DS, i.e., includes all IDDs, and has been unsuccessful in increasing short-term (≤ 12 wks.) or long-term MVPA (12 mos.). Results from our 12-wk. pilot trial of a remote method which delivers real-time MVPA, led by a trained health educator, to groups of adults with DS in their homes (n=27), via video conferencing on a tablet computer demonstrated high attendance, increased MVPA during group sessions, and improvements in cognitive function. However, the sustainability, impact on total daily MVPA, optimal session frequency, and potential impacts on cognitive function and measures of brain health of remotely delivered group MVPA sessions in adults with DS are unknown.

Therefore, we will conduct a 12 mo. early stage clinical trial in 80 non-demented adults with DS to determine the feasibility and potential efficacy of remotely delivered group MVPA, delivered at two different frequencies to increase daily MVPA, relative to a usual care control. This early stage clinical trial will inform and advance the design of a subsequent late stage clinical trial while providing important data regarding the effect of MVPA on cognition and measures of brain health related to development of AD in adults with DS.

3 STUDY DESIGN

This is a 12-mo. randomized control trial in 80 non-demented adults with DS. Participants will be randomized (2:2:1) to attend 40 min. remotely delivered group MVPA sessions (Zoom™ Video Conferencing Inc., San Jose, CA) at a low frequency (1 session/wk., RL) or high frequency (3 sessions/wk., RH), or a usual care control (UC). In addition to the group MVPA sessions, participants in both the RL and RH arms will receive a step counter (Charge 3™, Fitbit, San Francisco, CA), access to resources for increasing MVPA, and one 20-min remotely delivered (Zoom™) individual support/education session/wk. Content for both the RL and RH arms will be identical with the exception of group MVPA session frequency (1 vs. 3/wk.). Participants in the UC arm will receive a step counter (Charge 3™, Fitbit, San Francisco, CA), access to resources for increasing MVPA, and monthly remote (Zoom™) individual support/education. The primary outcomes, daily MVPA will be assessed by portable accelerometer (ActiGraph wGT3XBT, ActiGraph LLC, Pensacola, FL) at baseline, 3, 6, 9 and 12 mos. The secondary outcomes, cardiovascular fitness, quality of life, cognitive function and brain parameters related to AD (whole and regional brain volume, functional connectivity, cerebral blood flow) will be assessed at baseline, 6, and 12 mos. With the exception of assessment of daily MVPA by accelerometer, all outcomes will be assessed at the University of Kansas Medical Center, in Kansas City, KS. The exercise intervention will take place in the participants home.

| Table 1: Design Overview | | | |
|--|-------------------------------|------------------------------|------------------------------|
| | Intervention Arms | | |
| | Remote High (n=32) | Remote Low (n=32) | Usual Care (n=16) |
| MVPA recommendation | 150 min/wk. | 150 min/wk. | 150 min/wk. |
| Group MVPA sessions | Yes | Yes | No |
| Delivery format | Zoom™ video conferencing | Zoom™ video conferencing | NA |
| Frequency | 3d/wk. | 1d/wk. | NA |
| Intensity | ≥ 3 METS | ≥ 3 METS | NA |
| Duration | 40 min | 40 min | NA |
| Content | Stretch/aerobic activity/RE | Stretch/aerobic activity/RE | NA |
| Access to PA resources | Yes | Yes | Yes |
| MVPA Self-monitoring | Fitbit | Fitbit | Fitbit |
| Education/support/feedback sessions | Yes | Yes | Yes |
| Participants | DS adult + Study Partner | DS adult + Study Partner | DS adult + Study Partner |
| Frequency | 2x/mo | 2x/mo | 2x/mo |
| Delivery format | Zoom™ | Zoom™ | Zoom™ |
| Duration | 20 min/session | 20 min/session | 20 min/session |
| Note: NA = not applicable, RE= resistance exercise | | | |

